1.0 BACKGROUND AND RATIONALE

1.1 Glioblastoma

Glioblastoma is the most common malignant primary brain tumor and one of the most devastating cancers (Johnson and O'Neill 2012). Between 2004 and 2007, there were 37,690 patients newly diagnosed with glioblastoma, with an estimated incidence rate of 3 cases per 100,000 people in the United States (Ostrom, et al. 2014). The current standard of care for glioblastoma includes maximal safe resection followed by radiotherapy (RT) and temozolomide. However, despite optimal multi-modality therapy, median progression-free survival (PFS) is less than 7 months, and median overall survival (OS) is less than 15 months (Stupp, et al. 2005). Effective treatment for recurrent glioblastoma is even more dismal. A meta-analysis of 8 phase II studies of different cytotoxic drugs or cytostatic agents on recurrent glioblastoma showed objective response rate (ORR, including both complete response and partial response) of 6%, median progression-free survival (PFS) of 9 weeks, and PFS at 6 months (PFS6) of 15%. Based on remarkable radiological response from two single-arm, non-comparative phase II studies, bevacizumab (BVZ), an anti-angiogenesis antibody, was approved by the Food and Drug Administration (FDA) for the treatment of recurrent glioblastoma (Friedman, et al. 2009; Kreisl, et al. 2009). However, the duration of response is relatively short with median PFS of 3-4 months and OS of 7-9 month (Piccioni, et al. 2014). A recent randomized study (EORTC 26101) showed that the addition of BVZ to lomustine (CCNU) improved PFS but failed to improve OS as compared to CCNU alone (Wilk, et al. 2015). Previously, two large randomized studies also showed that the addition of BVZ to standard RT and temozolomide failed to improve OS (Chinot, et al. 2014; Gilbert, et al. 2014).

New treatments for both newly diagnosed and recurrent glioblastoma are greatly needed.

1.2 Glioblastoma in the Elderly

The median age of patients at the time of diagnosis of glioblastoma is 64, with approximately 6000 new patients over the age of 65 diagnosed each year in the United States with glioblastoma. The prognosis for these patients is worse than for younger patients, both as a consequence of the biologic characteristics of these tumors and comorbidities that may compromise surgery, radiation, or chemotherapy. A retrospective study of Medicare claims data paired with the Surveillance, Epidemiology, and End Results (SEER) database indicated a median overall survival (OS) of 4 months for patients with glioblastoma aged >65 years, inclusive of all treatment modalities. A recent study, reported at ASCO 2016, in patients 70 years of age or older eligible for chemotherapy + radiation therapy, indicated a median survival of 9.2 months and progression-free survival of 5.3 months for patients receiving temozolomide + radiation as compared to 7.6 month median survival and progression-free survival of 3.9 months in the radiation alone arm.

1.3 Incompletely Resected Glioblastoma

Glioblastoma is a highly invasive tumor and, as a consequence, surgical cure of a glioblastoma is not achievable. Gross total resection, defined as resection of contrast-enhancing tumor, can be achieved in approximately 40% of patients and has clear benefit. The majority of glioblastoma patients, however, undergo incomplete resection and some of them receive biopsy only, which is due to diffuse tumor extension, involvement of functionally vital areas, and patient-related risk factors such as increased age and comorbidities.

1.4 Unmethylated Glioblastoma

Gene methylation is a DNA-based control mechanism that regulates gene expression. In cancer, gene promoter regions can have increased or decreased levels of methylation. This epigenetic modification to DNA blocks gene function, resulting in the protein encoded for by the gene not being produced or being produced at a diminished level.

O⁶-methylguanine-DNA methyltransferase (MGMT), is a DNA repair enzyme that plays a critical role in response to therapy. The loss of or silencing of MGMT expression makes glioblastoma cells more sensitive to alkylating drugs such as temozolomide and BCNU. Several studies have shown that approximately 40% to 45% of glioblastoma tumors exhibit MGMT gene methylation with this methylation making the tumor more likely to respond to temozolomide whose damaging effects are reversed by DNA repair enzymes, such as MGMT. Methylation of MGMT results in diminished levels or loss of MGMT expression. In glioblastoma, MGMT gene methylation status is predictive of an improved response to temozolomide, with improved survival and progression-free survival, when compared to patients with unmethylated MGMT.

Glioblastoma patients with unmethylated MGMT respond poorly to temozolomide, with a very minor improvement in median survival and progression-free survival.

1.5 Sensitizing Glioblastoma to Temozolomide

Currently, temozolomide represents the only systemic therapy that has been shown to improve OS for glioblastoma (Stupp, et al. 2005). A phase II study attempted to re-sensitize recurrent temozolomide-resistant glioblastoma (those who would recur while receiving temozolomide or within 2 months of the last treatment of temozolomide) using an O⁶-methylguanine-DNA methyltransferase (MGMT) inhibitor called O⁶-benzylguanine (OBG) (Quinn, et al. 2009). Since MGMT is an enzyme that repairs DNA damage by alkylating agents such as temozolomide, a MGMT inhibitor is thought to be a rational agent to re-sensitize glioblastoma to temozolomide. Unfortunately, combination of O⁶-benzylguanine and temozolomide did not show any evidence of significant re-sensitization: ORR of 3% (95% CI: 0-15%), PFS6 of 9% (95% CI: 2-21%), and median PFS of 7.5 weeks (95% CI: 4.2-7.9 weeks) (Quinn, et al. 2009).

[figure not shown]
1.6 Preclinical Data of Disulfiram for Temozolomide Sensitization

Disulfiram (DSF) is a FDA-approved oral medication that has been used for treating alcoholism since 1951. It inhibits aldehyde dehydrogenase (ALDH), which leads to accumulation of acetaldehyde in the blood after ingestion of alcohol. It has well-known safety profile for up to 3000 mg per day in the absence of alcohol consumption and has been shown to readily cross the blood-brain barrier (Faiman, et al. 1978; Suh, et al. 2006). Multiple preclinical *in vitro* studies have demonstrated promising activity against glioblastoma cells (Hothi, et al. 2012; Liu, et al. 2012; Lun, et al. 2016; Triscott, et al. 2012). Specifically, two independent high-throughput drug screening studies have identified DSF with potent and selective activity against large panels of patient-derived glioma stem-like cells (GSCs, a subset of glioblastoma tumor cells that have been shown to be more resistant to RT and chemotherapy) (Hothi, et al. 2012; Lun, et al. 2016).

1.6.1 *In Vitro* Data of Disulfiram for Temozolomide Sensitization

[figure not shown]
In addition to promising cytotoxicity against glioblastoma cells, DSF has also appeared to synergize with temozolomide. Triscott *et al.* showed that DSF is active against temozolomide-resistant glioblastoma cell lines and provided synergistic activity when combined with temozolomide. As seen in Figure 1, DSF remarkably sensitized glioblastoma cells that were relatively resistant to temozolomide treatment (Triscott, et al. 2012).

Figure 1

[figure not shown]
Using low passage patient-derived glioblastoma cells, [name] at Duke University observed that copper (Cu) could significantly enhance the cytotoxicity of DSF (Figure 2A-B) and confirmed that the DSF-Cu combination could dramatically increase the sensitivity of glioblastoma cells to temozolomide (Figure 2C-D).

Figure 2

Lun *et al.* recently demonstrated that DSF-Cu not only could increase the sensitivity temozolomide-naïve GSCs to temozolomide (Figure 3A) but also recurrent temozolomide-resistant GSCs (Figure 3B). In Figure 3B, BT73R and BT206R represented two temozolomide-resistant GSC models that were derived from recurrent orthotopic glioblastoma tumors after serial temozolomide exposure, which simulated the evolutionary development of recurrent temozolomide-resistant glioblastomas in clinical practice. Of great interest, DSF-Cu was able to produce synergistic effect in combination with temozolomide on these temozolomide-resistant cells (Figure 3B), suggesting that DSF-Cu can re-sensitize temozolomide-resistant GSCs to temozolomide again (Figure 3B). Lun *et al.* also confirmed that Cu is crucial for the anti-tumor effect of DSF (Figure 3A-B) (Lun, et al. 2016).

[figure not shown]
Figure 3

1.6.2 *In Vivo* Data of Disulfiram for Temozolomide Sensitization

Lun *et al.* further verified the synergistic effect of DSF-Cu using orthotopic glioblastoma models that were produced from the GSCs. As seen in Figure 4A and 4B, DSF-Cu alone had limited effect on mice implanted with temozolomide-sensitive GSCs. However, when given with temozolomide, the combination significantly improved survival of mice with orthotopic tumors as compared to temozolomide alone. Furthermore, as seen in Figure 4C, the combination of DSF-Cu and temozolomide also significantly improved survival of mice implanted with temozolomide-resistant BT73R cells as compared to temozolomide alone or DSF-Cu alone (either treatment alone was ineffective) (Lun, et al. 2016). Altogether, these experiments provided proof of concept that DSF-Cu can (re)-sensitize temozolomide-resistant glioblastoma tumors to temozolomide and the combination of both would be required to observe the maximal anti-tumor effect.

Figure 4

1.6.3 Mechanism of DSF's Anticancer Activity

The mechanism of DSF's anti-cancer property is not definitively understood. Multiple studies have suggested that it may be due to the inhibition of chymotrypsin-like proteasome activity (Chen, et al. 2006; Cvek, et al. 2008; Hothi, et al. 2012). Others have showed that DSF-Cu complex can induce intracellular reactive oxygen species to trigger intrinsic apoptosis of glioblastoma cells through activation of c-Jun amino-terminal kinases (JNK) and p38 pathways (Liu, et al. 2012). **Paranjpe *et al.* showed that DSF increased the sensitivity of glioblastoma cells to temozolomide through inhibition of MGMT and demonstrated that DSF preferentially inhibited tumor MGMT in glioblastoma xenografts as compared to MGMT in the normal tissue (Paranjpe, et al. 2014).** Lun *et al.* demonstrated that proteasome inhibition was not responsible for all the cytotoxicity of DSF-Cu. Complete proteasome inhibition using proteasome inhibitor bortezomib did not produce the same level of cell death as DSF-Cu, while very low concentration of DSF-Cu with minimal proteasome inhibition was able to produce significant cytotoxicity.

Lun *et al.* also showed that DSF-Cu inhibited DNA repair pathways and thus enhanced the effects of DNA alkylating agents and radiation to increase DNA damage (Lun, et al. 2016). These data suggest that the mechanism of DSF against glioblastoma may be multifactorial and may be more likely to overcome temozolomide-resistance than a pure MGMT inhibitor such as O⁶-benzylguanine.

1.8 Drug Metabolism and Pharmacokinetics

After oral ingestion, DSF is partially reduced to diethyldithiocarbamate (DDTC) in the acidic stomach, which in turn forms a complex with Cu to form Cu(DDTC)₂. Both the parent DSF and Cu (DDTC)₂ are absorbed through the gastrointestinal tract. Generally, more than 80% of an oral dose is absorbed. Enteric formulation and oil may enhance absorption. After absorption, DSF is again reduced to DDTC and then Cu (DDTC)₂. Downstream metabolites also include diethylamine, carbon disulfide, diethyldithiomethylcarbamate (Me-DDTC), and glucuronic acid of DDTC. Me-DDTC is biotransformed into active inhibitors of ALDH (Johansson 1992). Experiments with radiolabeled DSF have shown distribution in the blood, liver, kidney, heart, adrenal gland, thyroid, pancreas, testes, spleen, marrow, muscles, and, most importantly, brain (Faiman, et al. 1978).

Previous pharmacokinetic studies were done on alcoholic patients after either single dose or repeated doses for 12 consecutive days. Apparent half-lives of DSF, DDTC, and Me-DDTC were 7.3, 15.5, and 22.1 hours, respectively. Average time to reach maximal plasma concentration was 8-10 hours for DSF and its metabolites. The mean peak plasma concentrations of DSF and Me-DDTC were 1.3 nM and 4.7 nM, respectively.

However, there was marked inter-subject variability in the plasma concentrations (Faiman, et al. 1984; Jensen, et al. 1982). Doses as low as 100 mg of DSF could produce detectable plasma concentrations of Me-DDTC and complete blockade of ALDH activity in erythrocytes (Johansson, et al. 1991). As seen in Figure 1, three daily doses of DSF will allow for DSF and its metabolites to reach steady state.

Figure 1: Predicted pharmacokinetic profile of DSF and its metabolites (DDTC & Me-DDTC)

The metabolites of DSF are mainly excreted via kidneys, feces, and the lungs. Up to 20% of an oral dose may not be absorbed and thus excreted in the feces. About 65% is eliminated through the kidneys, mostly as the glucuronide of DDTC and inorganic sulfates. The metabolite carbon disulfide is mostly eliminated via the lungs (Johansson 1992).

In the blood, both DSF and Me-DDTC are mostly bound to albumin, with average binding percentages of 96 and 80% over the ranges 200-800 and 345-2756 nM, respectively. The average number of binding sites was approximately one for both substances, suggesting a single binding site for both. The average association constants were 7.1×10^4 and $6.1 \times 10^3 \text{ M}^{-1}$, respectively. Therefore, patients with impaired protein synthesis and decreased albumin levels may have considerably different plasma concentration of DSF and its metabolites. Both DSF and Me-DDTC are also very lipophilic, with Log P (octanol-water partition coefficient) of 2.81 and 1.85, respectively (Johansson 1990), which support their ability to cross the blood brain barrier.

1.9 Toxicology and Safety

DSF has been used clinically to treat alcoholism for more than 60 years, so its safety profile is well known. Early toxicology studies done in mice, rats, dogs, and rabbits have shown that DSF has very low toxicity, with LD_{50} between 1.8-10g/kg when administered orally.

At those extreme doses, demyelination of brain and spinal cord was observed on histopathology (Child and Crump 1952). Interestingly, long-term administration of high doses of DSF to rats did not induce any laboratory or histological signs of liver damage (Milandri, et al. 1980). High doses of DSF (up to 6 g daily) are relatively nontoxic in humans. Symptoms of overdose include vomiting, headache, apathy, ataxia, motor restlessness, irritability, hallucinations, psychosis, loss of consciousness and convulsions. Death occurs by respiratory arrest, preceded by ascending paralysis, and pathological lesions are seen in the liver, spleen, kidney and CNS, with congestion in the adrenal gland and edema in the heart muscle.

The current FDA-recommended dose of DSF is 250-500 mg daily for alcohol abstinence. In early clinical practice, a much higher dose of 1000-3000 mg per day was used (Fuller and Gordis 2004). At high dosages, the DSF-ethanol reaction may be severe and even fatal, but such high dosage in the absence of alcohol is well tolerated. In the early 1950s, 4 patients (out of an estimated 11,000 patients prescribed high doses of DSF) died of sudden respiratory or cardiovascular causes likely related to the DSF-ethanol reaction (Jacobsen 1952). At such high dosages, there were also case reports of psychosis in the absence of alcohol ingestion (Guild and Epstein 1951; Martensen-Larsen 1951). A phase I study administered a single dose of oral DSF prior to cisplatin every 3 weeks and encountered dose-limiting reversible confusion at 3000 mg/m² (approximately 4800 mg) (Stewart, et al. 1987). High doses of DSF may inhibit cerebrospinal dopamine B-hydroxylase (Nilsson, et al. 1987), and people with very low activity of dopamine hydroxylase may be prone to transient psychosis with such inhibition (Major, et al. 1979). In another phase I study of non-metastatic recurrent prostate cancer patients treated with 250-500 mg of DSF alone, grade 3 toxicities included double vision, hearing loss, LFT abnormality, diarrhea, constipation, and ataxia (Schweizer, et al. 2013).

In a previous phase I study of 500-1000 mg DSF in combination with adjuvant temozolomide in newly diagnosed glioblastoma patients after chemoradiotherapy, grade 2-3 toxicities that were attributed to DSF included delirium, ataxia, dizziness, neuropathy, and fatigue (Table 1). Higher dose of 1000 mg DSF per day could not be tolerated due to relatively fast onset of delirium and ataxia within the first month of therapy. Therefore, it was determined that 500 mg per day of DSF is the MTD in combination with adjuvant temozolomide. However, even at the MTD of 500 mg per day, 2 of 7 patients eventually stopped DSF due to possibly DSF-related toxicity. One patient developed grade 3 delirium after 55 days of DSF; another patient developed grade 3 motor neuropathy (lower extremity weakness and foot drop). Both toxicities resolved after discontinuing DSF (Huang, et al. 2016).

Table 1: Possible DSF-related toxicity during Adjuvant temozolomide

Toxicities [*]	DSF 500 mg (n=7)		DSF 1000 mg (n=5)	
	Grade 2	Grade 3	Grade 2	Grade 3
Ataxia	1 (14%)	0	2 (40%)	1 (20%) [†]
Delirium	0	1 (14%) [†]	2 (40%)	2 (40%) [§]
Dizziness	1 (14%)	0	1 (20%)	0
Fatigue	3 (43%)	0	1 (20%)	0
Peripheral motor neuropathy	0	1 (14%) [†]	1 (20%)	0
Peripheral sensory neuropathy	2 (29%)	0	1 (20%)	0

^{*}Grade 2-3 adverse events according to the National Cancer Institute Common Terminology Criteria for Adverse Events (NCI CTCAE) v. 4.0 (2009) that were possibly or probably related to DSF and that were not present at baseline.

[†]Not dose-limiting toxicity as occurred after the first month of DSF.

[§]Dose-limiting toxicity as occurred within the first month of DSF.

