4.3 Study Evaluations

Consistent with standard of care, patients will be seen approximately every 4 weeks. At each visit, a ECOG evaluation and corticosteroid usage (mg per day) will be recorded. Brain MRI will be obtained every 8 weeks to assess for radiological response. Quality of Life (QOL) will be assessed using the Edmonton Symptom Assessment System – Revised (ESAS-r) questionnaire. Subjects will be monitored for copper levels on Day 1 (+/- 7 days) of Cycle 1 and Cycle 4 of adjuvant temozolomide.

Patients are evaluated for adverse events for 30 days from the last treatment of DSF-Cu, or until death, whichever occurs first. Patients removed from study for unacceptable adverse events will be followed until resolution or stabilization of the adverse event. Patients will also be removed from the study for non-compliance.

Table 2: Potential Adverse Events Related to DSF

MedDRA Term	Frequency: Likely: greater than 10% Less Likely: 1-10% Rare: 1% or less
Neoplasms	Rare: Tumor necrosis
Blood and lymphatic system disorders	Rare: Neutropenia, anemia, leukopenia, thrombocytopenia, lymphopenia (likely due to temozolomide)
Immune system disorders	Rare: Hypersensitivity
Metabolism and nutrition disorders	Likely: Alcohol intolerance, metallic or garlic-like aftertaste
Psychiatric disorders	Less Likely: psychosis, delirium (need to rule out tumor progression)
Nervous system disorders	Likely: Drowsiness, headache, confusion Less Likely: ataxia, gait disturbance, peripheral neuropathy Rare: Extrapyrarnidal symptoms
Eye disorders	Rare: Optic neuritis
Cardiac disorders	Less Likely: Tachycardia, hypotension (need to rule out DSF-alcohol reaction)
Respiratory, thoracic, and mediastinal disorders	Less Likely: Dyspnea (need to rule out DSF-alcohol reaction)
Gastrointestinal disorders	Likely: Nausea, vomiting, diarrhea Less Likely: constipation (likely due to temozolomide)
Hepatobiliary disorders	Rare: Hepatitis
Skin and subcutaneous tissue disorders	Less Likely: Allergic dermatitis
Musculoskeletal	Rare: Arthralgia, myalgia
Renal and urinary disorders	Rare: Dysuria, hematuria
Reproductive system	Less likely: impotence
General disorders	Likely: Fatigue

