4.4.3 Central Nervous System Effects

Doses of 500-1000 mg of DSF per day with adjuvant temozolomide produced neurological toxicities in some patients, including delirium/psychosis, ataxia, and peripheral neuropathy, especially at the 1000 mg dose. Patients should be carefully monitored for early signs of these symptoms. Once other causes such as tumor progression are ruled out, dose reduction of DSF to 125 mg (half of 250 mg tablet) once a day should be considered if the toxicity is grade 2 or greater (refer to Section 6.2). If symptoms are not improving with dose reduction, DSF should be discontinued. Patients whose symptoms are not considered immediately life-threatening should be carefully monitored. Each patient may be approached individually with a systematic assessment to rule out other causes. Appropriate tests may include vital signs measurement, computerized tomography, MRI scans, or other appropriate medical assessment.

If the patient's level of consciousness is considered to be life-threatening, the patient should be hospitalized and necessary measures should be instituted to secure the airway, ventilation, and intravenous access.

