4.5 Duration of Therapy

Patients demonstrating continued benefit from the adjuvant temozolomide after 6 cycles can continue treatment to a maximum of 12 cycles.

If at any time the constraints of this protocol are considered to be detrimental to the patient's health and/or the patient no longer wishes to continue protocol therapy, the protocol therapy should be discontinued and the reason(s) for discontinuation will be documented.

In the absence of treatment delays due to adverse events, DSF-Cu treatment may continue until:

- Documented and confirmed disease progression
- Death
- Adverse event(s) that, in the judgment of the investigator, may cause severe or permanent harm or which rule out continuation of study drug
- Patient develops unacceptable toxicity deemed possibly, probably, or definitely related to drug that does not resolved to grade 1 or to the patient's baseline status
- Patient requires more than 1 dose reductions
- General or specific changes in the patient's condition render the patient unacceptable for further treatment in the judgment of the investigator
- Serious noncompliance with the study protocol
- Lost to follow-up
- Patient withdraws consent
- Investigator removes the patient from study
- The investigator, or the investigator's institution decides to close the study

In the case of tumor progression, both temozolomide and DSF-Cu should be discontinued, and patient should be considered for second-line therapy. If temozolomide is temporarily withheld due to toxicity, DSF-Cu should be continued until temozolomide may be resumed again. If temozolomide is discontinued, DSF-Cu may be continued as per the discretion of the treating physician. If DSF-Cu is discontinued due to toxicity, temozolomide may be continued as per the discretion of the treating physician.

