5.0 RESPONSE ASSESSMENT

For the purposes of this study, patients should be evaluated for response approximately every 8 weeks.

Response and progression will be evaluated in this study using the updated RANO response assessment criteria for high-grade gliomas (Wen, et al. 2010).

Criteria for Determining First Progression Depending on Time from Initial Chemoradiotherapy

First Progression	Definition
Progressive disease < 12 weeks after completion of chemoradiotherapy	Progression can only be defined using diagnostic imaging if there is new enhancement outside of the radiation field (beyond the high-dose region or 80% isodose line) or if there is unequivocal evidence of viable tumor on histopathologic sampling (eg, solid tumor areas [ie, > 70% tumor cell nuclei in areas], high or progressive increase in MIB-1 proliferation index compared with prior biopsy, or evidence for histologic progression or increased anaplasia in tumor). Note: Given the difficulty of differentiating true progression from pseudoprogression, clinical decline alone, in the absence of radiographic or histologic confirmation of progression, will not be sufficient for definition of progressive disease in the first 12 weeks after completion of concurrent chemoradiotherapy.
Progressive disease ≥ 12 weeks after chemoradiotherapy completion	
 1. New contrast-enhancing lesion outside of radiation field on decreasing, stable, or increasing doses of corticosteroids. 2. Increase by ≥ 25% in the sum of the products of perpendicular diameters between the first post-radiotherapy scan, or a subsequent scan with smaller tumor size, and the scan at 12 weeks or later on stable or increasing doses of corticosteroids. 3. Clinical deterioration not attributable to concurrent medication or comorbid conditions is sufficient to declare progression on current treatment but not for entry onto a clinical trial for recurrence. 4. For patients receiving antiangiogenic therapy, significant increase in T2/FLAIR non-enhancing lesion may also be considered progressive disease. The increased T2/FLAIR must have occurred with the patient on stable or increasing doses of corticosteroids compared with baseline scan or best response after initiation of therapy and not be a result of comorbid events (eg, effects of radiation therapy,

First Progression	Definition
	demyelination, ischemic injury, infection, seizures, postoperative changes, or other treatment effects).

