Progression	
Defined by any of the following:
 
 • $\geq 25\%$ increase in sum of the products of perpendicular diameters of enhancing lesions compared with the smallest tumor measurement obtained either at baseline (if no decrease) or best response, on stable or increasing doses of corticosteroids*. The absolute increase in any dimension must be at least 5mm when calculating the products. • Significant increase in T2/FLAIR non-enhancing lesion on stable or increasing doses of corticosteroids compared with baseline scan or best response after initiation of therapy* not caused by comorbid events (e.g. radiation therapy, demyelination, ischemic injury, infection, seizures, postoperative changes, or other treatment effects). • Any new measurable lesion.

Response	Criteria
	
 • Clear clinical deterioration not attributable to other causes apart from the tumor (e.g. seizures, medication adverse effects, complications of therapy, cerebrovascular events, infection, and so on) or changes in corticosteroid dose. • Failure to return for evaluation as a result of death or deteriorating condition; or clear progression of non-measurable disease.

- NOTE. All measurable and non-measurable lesions must be assessed using the same techniques as at baseline.
- Abbreviations: MRI, magnetic resonance imaging; FLAIR, fluid-attenuated inversion recovery.
- Stable doses of corticosteroids include patients not on corticosteroids.

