10.0 STATISTICAL CONSIDERATIONS

10.1 Definition of Primary Endpoints and Analytical Plan

The co-primary endpoints will be ORR and PFS6. ORR will be defined as the percentage of patients with CR or PR according to the RANO criteria as described in Section 6.0. PFS6 will be defined as proportion of patients that are free from progressive disease (PD) as per RANO criteria or death at 6 months from the date of the first dose of DSF-Cu. PFS6 and median PFS will be estimated using the Kaplan-Meier product-limit method. For unmethylated glioblastoma receiving temozolomide without DSF-Cu, an ORR of less than 10% and PFS6 of less than 20% (Quinn, et al. 2009).

To justify future use of or drug development of DSF-Cu for glioblastoma, we hypothesized that the addition of DSF-Cu to temozolomide would improve ORR to 20% or increase PFS6 to 30%. The sample size is calculated based on the above hypotheses with one-sided exact test at an approximate α level of 0.10 and 80% statistical power. At these type I and II error rates, 14 -20 patients will detect a proportion of patients who have ORR significantly higher than 5% or PFS6 significantly higher than 10%. Of note, previous phase II study testing addition of O⁶-benzylguanine (a MGMT inhibitor) to temozolomide for temozolomide-resistant glioblastoma used similar hypothesis and observed a disappointing ORR of 3% and PFS6 of 9% (Quinn, et al. 2009). This negative phase II study has detailed information on ORR, PFS, and OS as well as associated estimated 95% CIs and will serve as a historical comparison for this study.

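### Whether a neurological decline without imaging progression is attributed to disulfiram or to tumour decides both PFS6 and the safety table, and the plan has no cross-check on that label

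*Combined protocol and SAP*

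**What the plan says.** **Phase I background.** Sections 1.7 and 1.9 describe delirium, ataxia and neuropathy with DSF at 500 to 1000 mg/day. At 500 mg/day, 2 of 7 patients stopped DSF, one for grade 3 delirium and one for weakness: "another patient developed grade 3 motor neuropathy (lower extremity weakness and foot drop). Both toxicities resolved after discontinuing DSF". The footnote to Table 1 classes the events as possibly or probably related. This trial gives 250 mg/day (Section 4.2).

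**Progression rules (Section 5.0).** In the first-progression table, from 12 weeks after chemoradiotherapy, "Clinical deterioration not attributable to concurrent medication or comorbid conditions is sufficient to declare progression on current treatment". Before 12 weeks, the same table says that clinical decline alone is not enough. The response-assessment table also lists as progression "Clear clinical deterioration not attributable to other causes apart from the tumor". It gives medication adverse effects among the other causes, but sets no time limit.

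**Toxicity rules.** Section 4.4.3, on central nervous system effects, says "Once other causes such as tumor progression are ruled out, dose reduction of DSF" should be considered at grade 2 or above. Table 2 in Section 4.3 attaches a similar condition to one entry only: "psychosis, delirium (need to rule out tumor progression". Section 6.3 allows a DSF reduction when the investigator judges an event at least possibly related, with no requirement to exclude progression first.

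**Consequences.** Section 4.5: "In the case of tumor progression, both temozolomide and DSF-Cu should be discontinued". Section 10.1 defines PFS6 by RANO progression or death at 6 months from the first DSF-Cu dose. Section 10.2 tabulates toxicities that are possibly, probably or definitely related to DSF.

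**The concern.** Delirium, gait disturbance or limb weakness in a glioblastoma patient may come from the tumour or from the drug. If the MRI does not show RANO progression, the label rests on the investigator's attribution, made with knowledge of treatment in a single-arm trial.

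That label moves two results at once. Called progression, the patient fails PFS6 and the event need not enter the DSF toxicity table. Called DSF toxicity, the event is tabulated and the patient stays progression-free unless imaging progression, a later clinical call or death follows before 6 months. The plan gives no default when neither cause can be excluded, no independent review, and no analysis showing how far the results depend on the choice. The back-dating rule in Section 5.1 covers suspected pseudoprogression only.

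**Working it through.** **1. The plan's own sample size.** Section 10.1 specifies a "one-sided exact test at an approximate α level of 0.10 and 80% statistical power" and says "14 -20 patients will detect a proportion of patients who have ORR significantly higher than 5% or PFS6 significantly higher than 10" per cent; the alternatives are ORR 20% and PFS6 30%. With X ~ Binomial(n, p) and success if X ≥ r, alpha = P(X ≥ r | p0) and power = P(X ≥ r | p1). The smallest n with alpha ≤ 0.10 and power ≥ 0.80 is:

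- PFS6, 10% against 30%: n = 18, r = 4, alpha 0.098, power 0.835.
- ORR, 5% against 20%: n = 21, r = 3, alpha 0.085, power 0.821.

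The upper end of 14 to 20 is within two patients of both results; the lower end is not reproduced. That is a separate matter and this point does not depend on it.

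**2. Baseline PFS6 rule.** The plan states no cut-off, so I take the smallest r with alpha ≤ 0.10 at p0 = 0.10.

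- n = 20: r = 5, alpha 0.043, power 0.762.
- n = 14: r = 4, alpha 0.044, power 0.645.

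**3. Weight of one label.** 1/20 = 5 percentage points; 1/14 = 7 percentage points.

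**4. One patient relabelled.** If one true success is called progression, the trial needs r + 1 true successes. If one true failure is kept as progression-free, it needs only r − 1.

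| n | Quantity | Formula | Baseline | After one relabelling |
|---|---|---|---|---|
| 20 | Power | P(X ≥ 6 given p = 0.30) | 0.762 | 0.584 |
| 14 | Power | P(X ≥ 5 given p = 0.30) | 0.645 | 0.416 |
| 20 | Alpha | P(X ≥ 4 given p = 0.10) | 0.043 | 0.133 |
| 14 | Alpha | P(X ≥ 3 given p = 0.10) | 0.044 | 0.158 |

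These figures need no assumed toxicity rate. The alpha figures are upper bounds, because MRI every 8 weeks (Section 4.3) would catch some true progressors before 6 months.

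**5. When a clinical-only call is possible.** Assume that DSF-Cu starts with chemoradiotherapy and that chemoradiotherapy ends on day 42. The first-progression table then bars a clinical-only call until day 42 + 84 = 126. Six months is about day 183, which leaves about 57 days, or 8 weeks. The response-assessment table has no such bar, so under it the whole 6 months is open.

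**6. Phase I rate.** 2/7 = 29%, exact 95% CI 3.7% to 71.0%, at twice this trial's daily dose. It does not fix a rate at 250 mg/day. Section 1.9 also cites grade 3 ataxia in a study of 250 to 500 mg, so the risk at this dose is not excluded.

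**The case against.** The strongest reply is that these passages describe an ordinary differential diagnosis. Section 4.4.3 calls for a systematic assessment, including imaging. The response-assessment table requires the deterioration to be clear and excludes medication effects. Section 4.5 speaks of documented and confirmed progression. PFS6 is to be estimated by Kaplan-Meier with no stated cut-off, so the power and alpha figures rest on a reconstructed rule.

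Much of this stands, and it rules out several stronger readings that a reader might infer:

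- **That the toxicity and progression rules deadlock.** They do not. Section 6.3 lets DSF be reduced on a possible relation, and Table 2's condition applies to psychosis and delirium only, not to ataxia or neuropathy.
- **That the phase I proves DSF causes these signs at this dose.** It reports possible or probable relation in 7 and 5 patients, at two to four times the daily dose.
- **That clinical-only progression is open throughout.** The first-progression table bars it for 12 weeks after chemoradiotherapy. Only the other table lacks the limit.
- **That power would fall to 0.43 at n = 20.** This assumes that 29% of true successes are miscalled, which carries over the 500 mg/day stopping rate and supposes that every such event is called progression. In the phase I both were attributed to DSF.
- **That alpha would reach 0.15 to 0.33 at n = 20.** This assumes that 5% to 10% of all failures are relabelled, including deaths and imaging progressions, which cannot be called toxicity. If only a quarter of failures could be relabelled and 10% of those were (both assumptions), p0 = 0.10 + 0.90 × 0.25 × 0.10 = 0.1225 and alpha is 0.089, still below 0.10.

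What the reply does not supply is a default label, or any analysis that shows the effect of the attribution. Section 6.3 governs dose, not whether the patient has progressed.

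**Conclusion.** The point holds in a limited form. A neurological decline without imaging progression can be labelled either way, and the same open-label judgement decides the patient's PFS6 status and whether the event is tabulated as toxicity. The documents do not show that this will be frequent, nor which direction the error would take.

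Its size is best given per patient: 5 to 7 points of PFS6, with power falling by 0.18 (n = 20) or 0.23 (n = 14) for one lost success, and alpha rising to at most 0.133 or 0.158 for one retained failure. The power and alpha figures assume a reconstructed exact rule at 10% against 30%. The 8-week window assumes that chemoradiotherapy ends on day 42.

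The change is worth making because the trial is small and the remedy nearly free.

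**What to change.** 1. **Section 10.2:** tabulate all delirium/psychosis, ataxia/gait disturbance and neuropathy events by grade whatever their attribution, with attribution as a column. Include events that were called clinical progression.
2. **Section 10.1:** keep RANO progression as the primary definition. Flag every progression call based on clinical deterioration alone, and every such neurological event attributed to DSF without imaging progression. Report PFS6 with all flagged cases counted as progression and with none so counted.
3. **Section 5.0:** reconcile the first-progression and response-assessment tables on whether clinical decline alone can be progression in the first 12 weeks after chemoradiotherapy.

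I would not reclassify progression according to recovery after DSF is stopped or reduced. That would depart from RANO, make the endpoint depend on how DSF was managed, and be confounded by corticosteroids or second-line therapy.

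The cost is slightly more tabulation and a PFS6 range that may look less favourable than a single estimate. No extra visits or scans are needed, and no treatment rule changes.
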